1 SYNOPSIS

Protocol Title: A Phase 1 Study of Cabiralizumab (BMS-986227, FPA008) Administered Alone or in Combination with Nivolumab (BMS-936558) in Advanced Malignancies

Study Phase: 1

Study Population:

Advanced solid tumors and hematologic malignancies who are refractory to or have relapsed after standard therapies, or have no known effective treatment.

Objectives and Endpoints:

Objective	Endpoint
Primary 
 To assess the safety and tolerability of cabiralizumab as monotherapy in subjects with advanced solid tumors. 	
 Incidence of AEs, SAEs, AEs meeting protocol-defined DLT criteria, AEs leading to discontinuation, death and laboratory abnormalities in monotherapy cohorts.
Secondary 
 To assess the safety of cabiralizumab in combination with nivolumab in subjects with advanced solid tumors and hematologic malignancies. To characterize the PK profile of cabiralizumab administered alone and in combination with nivolumab. To characterize the immunogenicity of cabiralizumab and nivolumab To assess the preliminary anti-tumor activity of cabiralizumab administered alone and in combination with nivolumab in subjects with advanced solid tumors. To assess the preliminary anti-tumor activity of cabiralizumab administered in combination with nivolumab in subjects with hematologic malignancies. 	
 Incidence of AEs, SAEs, AEs leading to discontinuation, death and laboratory abnormalities Summary measures of PK parameters (Section 9.5) of cabiralizumab Incidence of ADA to cabiralizumab and nivolumab BOR, DOR assessed per RECIST 1.1 by investigator BOR, DOR assessed per IMWG Response criteria by investigator

Abbreviations: ADA, anti-drug antibody AE, adverse event; DLTs, dose limiting toxicities; BOR, best overall response, DOR, duration of response; PK, pharmacokinetic; SAE, serious adverse event

Overall Design:

This study is a Phase 1, open-label, dose escalation study to evaluate the safety, tolerability, PK, PD and preliminary anti-tumor activity of cabiralizumab as monotherapy in subjects with advanced solid tumor. In addition, the study will evaluate the safety profile, PK, PD and preliminary anti-tumor activity of cabiralizumab in combination with nivolumab in subjects with advanced solid tumors and hematologic malignancies.

For the monotherapy cohorts of the study, cabiralizumab will be given on Day 1 of each 14-day treatment cycle until the progression of disease, discontinuation of toxicity, withdrawal of consent or study closure. For the combination cohorts of the study, cabiralizumab and nivolumab will be given on Day 1 of each 14-day treatment cycle until the progression of disease, discontinuation of toxicity, withdrawal of consent or study closure. Nivolumab will be administered as an IV infusion over 30 minutes, and then cabiralizumab will be administered as an IV infusion over 30 minutes. This study consists of 2 planned cabiralizumab monotherapy cohorts (M1: 2 mg/kg and M2: 4 mg/kg) and 2 cohorts of cabiralizumab in combination with nivolumab (C1: 4 mg/kg cabiralizumab and 3 mg/kg nivolumab in subjects with solid tumor and C2: 4 mg/kg cabiralizumab and 3 mg/kg nivolumab in subjects with hematologic malignancies). The study design schematic is presented in Figure 1 and Figure 2.

Figure 1: Dose Escalation Schema

[figure not shown]
[figure not shown]

Figure 2. Study Design Schema

A modified Toxicity Probability Interval (mTPI) design will be used to assess the tolerability of cabiralizumab in monotherapy. The DLT evaluation period begins on the first day of treatment and continues for 28 days. Participants who receive at least 2 doses of study drug during the 28-day evaluation interval or participants who discontinue study treatment for drug-related AEs before receiving 2 doses of study drug will be considered evaluable for DLT determination. Dose escalation will be based on the number of DLTs experienced during the DLT evaluation period as determined by the Investigators and Medical Monitor in consultation with Efficacy and Safety Review Committee.

Number of Participants:

This is a Phase 1 study and the sample size cannot be precisely determined and depends on the observed toxicities. Between 6 and 12 subjects are expected to be treated during dose escalation, assuming 2 mg/kg and 4 mg/kg cabiralizumab monotherapy are explored. On the combination cohorts, 6 subjects in each cohort are expected to be treated with 4 mg/kg cabiralizumab in combination with 3 mg/kg nivolumab following the dose escalation part of monotherapy. In addition, Sponsor has the option to expand combination cohorts (up to 12 subjects in total per each

combination cohort) at the dose previously established to be safe in order to obtain additional data or to investigate alternative dose levels.

Treatment Arms and Duration:

- Cohort M1: cabiralizumab 2 mg/kg will be administered every 2 weeks until progression of disease, discontinuation due to toxicity, withdrawal of consent, or study closure.
- Cohort M2: cabiralizumab 4 mg/kg will be administered every 2 weeks until progression of disease, discontinuation due to toxicity, withdrawal of consent, or study closure.
- Cohort C1/C2: cabiralizumab 4 mg/kg in combination with nivolumab 3 mg/kg will be administered every 2 weeks until progression of disease, discontinuation due to toxicity, withdrawal of consent, or study closure.

Study treatment:

Study Drug for CA025001		
Medication	Potency	IP/Non-IP
Cabiralizumab (BMS-986227) Solution for Injection	100 mg/vial (20 mg/mL)	IP
Nivolumab Solution for Injection	100 mg/vial (10 mg/mL)	IP

2 SCHEDULE OF ACTIVITIES

Table 2-1: Screening Procedural Outline (CA025001)		
Procedure	Screening Visit Within 28 days prior to treatment assignment	Notes
Eligibility Assessments		
Informed Consent	X	A participant is considered enrolled only when a protocol specific informed consent is signed.
Inclusion/Exclusion Criteria	X	
Medical History	X	Include any toxicities or allergy related to previous treatments.
Baseline Tumor Assessment	X	
Prior/Concomitant Medications	X	
Safety Assessments		
Physical Examination (PE)	X	If the screening PE is performed within 1 day prior to dosing on Day 1 then a single exam may count as both the screening and pre-dose evaluation.
Physical Measurements	X	Includes height and weight.
ECOG P.S.	X	
Assessment of Signs and Symptoms	X	
Vital Signs	X	Includes body temperature, respiratory rate, and blood pressure and heart rate (sitting or supine). Blood pressure and heart rate should be measured after the participant has been resting quietly for at least 5 minutes. Pulse oximetry is performed at rest and after exertion prior to nivolumab dosing at each dosing visit only for the combination cohorts. Refer to Section 9.4.2
Electrocardiogram (ECGs)	X	ECGs should be recorded after the participant has been supine for at least 5 minutes.

Table 2-1: Screening Procedural Outline (CA025001)

Procedure	Screening Visit Within 28 days prior to treatment assignment	Notes
Laboratory Tests	X	Hematology: CBC with differential, platelets, hemoglobin, hematocrit, RBC Chemistry: CK, AST, ALT, alkaline phosphatase, bilirubin (direct and total), BUN, calcium, chloride, creatinine, glucose, cholinesterase, LDH, phosphorus, potassium, sodium, albumin, amylase, lipase, thyroid panel (TSH, Free T3 and Free T4), PT/INR, PTT (aPTT) and Troponins Urinalysis: Glucose, Protein, Blood
Serology	X	Includes hepatitis C antibody, hepatitis B surface antigen/hepatitis B core antibody, and Interferon-Gamma Release Assays (e.g. Quantiferon test).
Pregnancy Test	X	For WOCBP only.
Follicle Stimulating Hormone (FSH)	X	Women only. Refer to Appendix 4 .
Baseline Tumor Assessment		
For Solid tumor : Tumor Assessments	X	Refer to Section 9.1.1
For Multiple Myeloma		Refer to Section 9.1.2
Myeloma Urine and Serum Lab tests (SPEP/UPEP/sFLC)	X	
Bone Marrow Aspiration/Biopsy	X	Refer to Table 9.1.2.1-1
Skeletal survey	X	
Documentation of extramedullary soft tissue plasmacytomas, if clinically indicated	X	Perform CT or MRI at screening if clinically indicated or if patient had a previous extramedullary or bone plasmacytoma.
[REDACTED]	[REDACTED]	[REDACTED]

Table 2-1: Screening Procedural Outline (CA025001)

Procedure	Screening Visit Within 28 days prior to treatment assignment	Notes
Adverse Event Reporting		
Monitor for Serious Adverse Events	X	All SAEs must be collected from the date of participant's written consent

Table 2-2: Treatment Phase Procedural Outline (CA025001)

Procedure	Cycle ^a 1				Cycle 2~	EOT ^b	Follow-up Period 28 days and 100 days post-last dose	Notes
	D 1	D 2	D 4	D 8				
Safety Assessments								
Physical Examination (PE)	X			X	X	X	X	
ECOG P.S.	X				X	X	X	
Physical Measurements ^c	X				X	X	X	Weight only Within 72 hours prior to dosing.
Vital Signs	X			X	X	X	X	See note in screening procedures and Section 9.4.2 . Cohort C1, C2: measure Pulse oximetry at rest and after exertion prior to nivolumab dosing
Electrocardiogram (ECGs) Refer to the DM ECG Study Guidelines	X				C2D1	X		See note in screening procedures and Section 9.4.3 . Pre dose and within 1 hour of completion of cabiralizumab dosing on C1D1 and C2D1
Laboratory Tests ^c	X			X	X	X	X	See note in screening procedures and Section 9.4.4 . Pre-dose on Day 1 on each cycle. Within 72 hours prior to dosing.
Pregnancy Test ^c	X				X	X	X	Every 2 cycles D1 within 72 hours prior to dosing
Adverse Event Reporting	X							

Table 2-2: Treatment Phase Procedural Outline (CA025001)

Procedure	Cycle ^a 1				Cycle 2~	EOT ^b	Follow-up Period 28 days and 100 days post-last dose	Notes		
	D 1	D 2	D 4	D 8	D 1					
Monitor for Non-Serious Adverse Events	X									
Monitor for Serious Adverse Events	X							All SAEs must be collected from the date of participant's written consent until 100 days of discontinuation of dosing		
Concomitant Medications Collection	X									
Pharmacokinetic (PK)/ADA Assessments										
Serial Blood PK Sampling	X	X	X	X	X ^d	X	X	See Section 9.5.		
ADA sampling	X				X ^e	X	X	See Section 9.5.		
Efficacy Assessments										
Tumor Assessments (for Solid tumor)	X					X ^f	Every 8 weeks (\pm 7 days) for first 48 weeks, then every 12 weeks (\pm 7 days) thereafter See Section 9.1.1			
For Multiple Myeloma										

Table 2-2: Treatment Phase Procedural Outline (CA025001)

Procedure	Cycle ^a 1				Cycle 2~ D 1	EOT ^b	Follow-up Period 28 days and 100 days post-last dose	Notes				
	D 1	D 2	D 4	D 8								
Myeloma Urine and Serum Lab tests (SPEP/UPEP/sFLC)	X				X ^f		Day 1 on every 2 cycles starting from C3D1					
Bone Marrow Aspiration/Biopsy	For confirmation of CR/sCR if applicable or, if clinically indicated at time of suspected disease progression											
Skeletal survey	If clinically indicated											
Documentation of extramedullary soft tissue plasmacytomas, if clinically indicated	As clinically indicated and at the time of CR/sCR assessments											
Flow Cytometry	For confirmation of CR/sCR if applicable or, if clinically indicated at time of suspected disease progression											
Subsequent Treatment (Anti-cancer)					X							
Survival Status					X							
Clinical Drug Supplies												
Study Drug Administration ^g	X				X		Those supplied by BMS					

^a Each cycle is 14-days.

^b End of treatment (EOT) is defined as the visit where the decision is made to discontinue the participant from treatment.

^c Physical measurements and laboratory tests do not need to be repeated if completed within the last 72 hours

^d Cycles 2-9, 13, 21

^e Cycles 2, 3, 5, 9, 13, 21

^f Only participants who have not discontinued study treatment for progressive disease.

^g Every 14 days (2days), subjects may be dosed no less than 12 days from the previous dose.

4 OBJECTIVES AND ENDPOINTS

Table 4-1: Objectives and Endpoints

Objectives	Endpoints
Primary 
To assess the safety and tolerability of cabiralizumab as monotherapy in subjects with advanced solid tumors.	
Incidence of AEs, SAEs, AEs meeting protocol-defined DLT criteria, AEs leading to discontinuation, death and laboratory abnormalities in monotherapy cohorts
Secondary 
To assess the safety of cabiralizumab in combination with nivolumab in subjects with advanced solid tumors and hematologic malignancies.To characterize the PK profile of cabiralizumab administered alone and in combination with nivolumab.To characterize the immunogenicity of cabiralizumab and nivolumabTo assess the preliminary anti-tumor activity of cabiralizumab administered alone and in combination with nivolumab in subjects with advanced solid tumors.To assess the preliminary anti-tumor activity of cabiralizumab administered in combination with nivolumab in subjects with hematologic malignancies.	
Incidence of AEs, SAEs, AEs leading to discontinuation, death and laboratory abnormalitiesSummary measures of PK parameters (Section 9.5) of cabiralizumabIncidence of ADA to cabiralizumab and nivolumabBOR, DOR assessed per RECIST 1.1 by investigatorBOR, DOR assessed by IMWG Response criteria by investigator
	

5 STUDY DESIGN

5.1 Overall Design

This study is a Phase 1, open-label, dose escalation study to evaluate the safety, tolerability, PK, and PD and preliminary anti-tumor activity of cabiralizumab as monotherapy in subjects with advanced solid tumor. In addition, the study will evaluate the safety profile, PK, PD and preliminary anti-tumor activity of cabiralizumab in combination with nivolumab in subjects with advanced solid tumors and hematologic malignancies.

For the monotherapy cohorts of the study, cabiralizumab will be given on Day 1 of each 14-day treatment cycle until the progression of disease, discontinuation of toxicity, withdrawal of consent or study closure. For the combination cohorts of the study, cabiralizumab and nivolumab will be given on Day 1 of each 14-day treatment cycle until the progression of disease, discontinuation of toxicity, withdrawal of consent or study closure. Nivolumab will be administered as an IV infusion over 30 minutes, and then cabiralizumab will be administered as an IV infusion over 30 minutes.

This study consists of 2 planned cabiralizumab monotherapy cohorts (M1: 2 mg/kg and M2: 4 mg/kg) and 2 cohorts of cabiralizumab in combination with nivolumab (C1: 4 mg/kg

cabiralizumab and 3 mg/kg nivolumab in subjects with solid tumor and C2: 4 mg/kg cabiralizumab and 3 mg/kg nivolumab in subjects with hematologic malignancies).

The study will consist of 3 periods: Screening, Treatment and Follow-up. The study will end after the last subject completes the last visit.

Screening begins by establishing the subject's initial eligibility and signing of the informed consent form (ICF). Subjects must have treatment assignment within 28 days after signing the informed consent.

The Treatment Phase begins when the treatment cohort is assigned to the subjects. The subject will be assigned to the open cohort (M1, M2, C1, or C2) at the timing of the treatment assignment. First dose should be started within 3 days of treatment assignment. The subjects will be required to be hospitalized for safety evaluation at least for 8 days from the first dose. The subjects can be discharged at the investigator's discretion at Day 8.

The Follow-Up Phase begins when the decision to discontinue a subject from all treatment is made. Subjects will be followed for drug-related toxicities until these toxicities resolve, return to baseline, or are deemed irreversible. All adverse events will be documented for a minimum of 100 days after the last dose of study medication. The study design schematic is presented in Figure 5.1-1 and Figure 5.1-2.

Figure 5.1-1: Dose Escalation Schematic

[figure not shown]
[figure not shown]

Figure 5.1-2: Study Design Schematic

5.1.1 Cabiralizumab monotherapy dose escalation

Enrollment of subjects in dose escalation part will be guided by the mTPI design. The study design sets a 25% target DLT rate with an equivalence interval of 20 - 30%. Doses of cabiralizumab to be explored in this part of the study will be 2 mg/kg and 4 mg/kg. Decisions regarding dose escalation will be guided by the incidence of DLTs (see [Section 5.1.2](#)) occurring within the DLT

evaluation period (28-days) based on the modified Toxicity Probability Interval (mTPI) design. Subjects will be enrolled in successive cohorts of 3 or 6 subjects. The first 3 subjects will receive 2 mg/kg of cabiralizumab every 2 weeks. A decision to proceed to the next higher dose level (4 mg/kg), to add 3 subjects at 2 mg/kg cohort or to stop the enrollment will be made once the first 3 subjects have completed DLT evaluation period. Guided by mTPI, the dose escalation needs to be agreed by the Efficacy and Safety Evaluation Committee after clinical assessment of the totality of available safety data from all treated participants. An additional dose level may also be evaluated if agreed upon by the Investigators, the Sponsor/Medical Monitor and the Efficacy and Safety Evaluation Committee. The performance of the design is reported in [Appendix 5](#). Basically 3 or 6 subjects will be enrolled in a cohort. However, if additional subject will be enrolled in a cohort (e.g. 4 or 7 subjects), dose escalation will be guided by [Table 1](#) in the Appendix 5.

Table 5.1.1-1: Guidance for Dose Escalation/De-escalation Based on Observed Toxicity Outcomes

		Number of Subjects Treated	
		3	6
Number of Subjects with DLTs	0	E	E
	1	S	E
	2	D	S
	3	DU	D
	≥ 4		DU

At Starting dose (2 mg/kg):

E: The current dose level is safe. Escalate and enroll subjects to the next higher dose level (4 mg/kg). If the next higher dose level (4 mg/kg) is deemed to be unacceptably toxic (DU) or has already enrolled 6 or more subjects with D, accept the current dose (2 mg/kg).

S: If 6 or more subjects have already enrolled at this dose level, accept the current dose level (2 mg/kg). Otherwise, stay current dose and enroll 3 additional subjects.

D/DU: The current dose (2 mg/kg) is toxic, stop the enrollment.

At Maximum dose (4 mg/kg):

E: The current dose level is safe. Accept the current dose (4 mg/kg).

S: If 6 or more subjects have already enrolled at this dose level, accept the current dose level (4 mg/kg). Otherwise, stay current dose and enroll 3 additional subjects.

D: De-escalate to the lower dose level (2 mg/kg). Accept the lower dose level (2 mg/kg) if 6 or more subjects have already been enrolled at the lower dose level (2 mg/kg).

DU: The current dose is unacceptably toxic. De-escalate to the lower dose level (2 mg/kg) without re-escalation to the current dose level (4 mg/kg). Accept the lower dose level (2 mg/kg) if 6 or more subjects have already been enrolled at the lower dose level (2 mg/kg).

5.1.1.1 *Dose Limiting Toxicity*

Non-Hematologic DLT

A DLT is defined as a study drug-related Non-Hematologic \geq Grade 3 AE (using National Cancer Institute [NCI] Common Terminology Criteria for Adverse Events [CTCAE] v 4.0) occurring during the first 28-days, excluding:

- Grade 3 tumor flare (defined as local pain, irritation, or rash localized at sites of known or suspected tumor),
- Grade 3 rash,
- Grade 3 immune-related adverse event (irAE) that resolved to a Grade 1 or less within 14 days, or a transient (resolving within 6 hours of onset) Grade 3 infusion-related AE.
- Grade 3 or 4 increase in amylase and/or lipase that is not associated with symptoms or clinical manifestations of pancreatitis.
- In the absence of clinical symptoms and other accompanying changes in bilirubin or ALT (as noted in [appendices 6, 7 and 8](#)), serum elevations of AST/ALT $> 12 \times \text{ULN}$ and $\leq 20 \times \text{ULN}$ that last for < 7 days will not be considered a DLT and serum elevations of CK and/or LDH $> 15 \times \text{ULN}$ and $\leq 20 \times \text{ULN}$ that last for < 7 days will not be considered a DLT.

Any recurrence of Grade 3 rash, Grade 3 immune-related AE, or Grade 3 infusion-related AE will be considered a DLT. An irAE is defined as a clinically significant AE that is associated with study drug exposure, of unknown etiology, and is consistent with an immune-mediated mechanism.

Definition of Hematologic DLT

Any of the following study drug-related AEs will be considered a hematologic DLT:

- Febrile neutropenia meeting the following criteria: body temperature $\geq 38.3^{\circ}\text{C}$ at a single measurement, or hyperthermia $\geq 38^{\circ}\text{C}$ with duration ≥ 1 hour AND neutrophil count $< 500/\text{mm}^3$ or $< 1,000/\text{mm}^3$ and predicted to decrease to $< 500/\text{mm}^3$ within 48 hours
- Grade 4 neutropenia that lasts > 5 days
- Grade 4 thrombocytopenia
- Grade 4 anemia
- Grade 3 thrombocytopenia associated with clinically significant bleeding
- Grade 3 or 4 hemolysis
- Hemotoxicities requiring red blood cell or platelet transfusions.

If the events described above or any other clinically significant events occur, these events will be discussed by the investigator, Sponsor/Medical Monitor and the Efficacy and Safety Review Committee to determine whether they qualify as DLT considering its clinical significance.

Participants who receive at least two doses of study drug during the 28-day evaluation interval or participants who discontinue study treatment due to study drug-related AEs before receiving two doses of study drug will be considered as evaluable for DLT determination.

If doses of cabiralizumab are delayed for more than 28 days during the DLT evaluation period because of study drug related AEs, the Investigator and Sponsor/Medical Monitor will consult the Efficacy and Safety Review Committee and decide whether such events should be classified as a DLT or not, and whether subjects with such events should be considered to be “evaluable” or not.

Unevaluable subjects may be replaced at the same dose level. Subjects who miss a dose during the DLT evaluation period may continue on treatment if the subject does not otherwise meet the criteria for permanent discontinuation in [Section 8](#).

Subjects who withdraw from the study during the DLT evaluation period for reasons other than a DLT are not evaluable for DLT and are replaced at the same dose level. The dose escalation to the next dose level and initiation of combination cohort should be determined in consideration of all safety information, including information on adverse events occurred in subjects excluded from DLT evaluation.

5.1.2 *Cabiralizumab in Combination with nivolumab:*

After tolerability of a dose of 4 mg/kg cabiralizumab monotherapy has been confirmed in the DLT evaluation period of the study, combination cohorts for both subjects with solid tumor and subjects with hematologic malignancies will open in parallel. 6 subjects per each cohort will be enrolled. The start of combination cohorts needs to be agreed by the Efficacy and Safety Evaluation Committee. Subjects will undergo screening evaluations to determine eligibility within 28 days prior to the first doses of cabiralizumab and nivolumab on Day 1 of Cycle 1. Cabiralizumab at a dose of 4 mg/kg and nivolumab at a dose of 3 mg/kg will be administered every 2 weeks.

Sponsor has the option to expand the combination cohorts in order to obtain additional data or to investigate alternative dose levels to those defined in the protocol. Upon completion of 28 days follow-up from the first dose on initial 6 subjects on each combination cohort and after agreed by the Efficacy and Safety Evaluation Committee, up to 24 patients (12 patients with advanced solid tumor and 12 patients with hematologic malignancies) may be enrolled in combination cohorts to fully characterize safety, PK, and PD.

5.1.3 *Data Monitoring Committee and Other External Committees*

[figure not shown]
Efficacy and Safety Review Committee will be established in this study.

5.2 *Number of Participants*

Between 6 and 12 subjects are expected to be treated during dose escalation, assuming 2 mg/kg and 4 mg/kg cabiralizumab monotherapy are explored. On the combination cohorts, 6 subjects each cohort are expected to be treated with 4 mg/kg cabiralizumab in combination with 3 mg/kg nivolumab following the dose escalation part of monotherapy. In addition, Sponsor has the option to expand combination cohorts (up to 12 subjects in total per each combination cohort) at the dose previously established to be safe in order to obtain additional data or to investigate alternative dose levels to those defined in the protocol.

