9.2.5 Pregnancy

If, following initiation of the study treatment, it is subsequently discovered that a participant is pregnant or may have been pregnant at the time of study exposure, including during at least 5 half-lives (5 months) after product administration, the investigator must immediately notify the BMS Medical Monitor/designee of this event and complete and forward a Pregnancy Surveillance Form to BMS Designee within 24 hours of awareness of the event and in accordance with SAE reporting procedures described in [Appendix 3](#).

In most cases, the study treatment will be permanently discontinued in an appropriate manner (e.g., dose tapering if necessary for participant safety). Please call the BMS Medical Monitor within 24 hours of awareness of the pregnancy.

Protocol-required procedures for study discontinuation and follow-up must be performed on the participant.

Follow-up information regarding the course of the pregnancy, including perinatal and neonatal outcome and, where applicable, offspring information must be reported on the Pregnancy Surveillance Form.

Any pregnancy that occurs in a female partner of a male study participant should be reported to Sponsor or designee. In order for Sponsor or designee to collect any pregnancy surveillance information from the female partner, the female partner must sign an informed consent form for disclosure of this information. Information on this pregnancy will be collected on the Pregnancy Surveillance Form.

9.2.6 *Laboratory Test Result Abnormalities*

The following laboratory test result abnormalities should be captured on the nonserious AE CRF page or SAE Report Form electronic, as appropriate. Paper forms are only intended as a back-up option when the electronic system is not functioning.

- Any laboratory test result that is clinically significant or meets the definition of an SAE
- Any laboratory test result abnormality that required the participant to have study treatment discontinued or interrupted
- Any laboratory test result abnormality that required the participant to receive specific corrective therapy

It is expected that wherever possible, the clinical rather than laboratory term would be used by the reporting investigator (e.g., anemia versus low hemoglobin value).

9.2.7 *Potential Drug Induced Liver Injury (DILI)*

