APPENDIX 6 AE MANAGEMENT FOR CABIRALIZUMAB MONOTHERAPY COHORTS

Hepatic Adverse Event Management without Liver Metastasis		
Grade of Liver Test Elevation	Management	Follow-Up
AST or ALT $>3.0 \times \text{ULN}$ and Total bilirubin $>2 \times \text{ULN}$ or INR > 1.5	
 – Discontinue cabiralizumab therapy per protocol 	
 – Continue LFT monitoring per protocol until resolution. – Continue monitoring for and other associated clinical signs or symptoms – Contact the Medical Monitor – Evaluate for non-drug related causes of the laboratory abnormalities (e.g. obstruction, viral infection, Gilbert's disease, etc) – Under selected circumstances (e.g alternative etiology is identified), patient may receive additional therapy only after consultation and agreement between the Sponsor/MM and the investigator if receiving additional treatment with cabiralizumab is in the best interest of the patient (e.g if the subject has demonstrated a response to therapy)
AST or ALT > 5 to $\leq 12 \times \text{ULN}$ and Total bilirubin $\leq 2 \times \text{ULN}$	
 – Continue cabiralizumab therapy if there are no clinical signs of significant muscle or hepatic damage – Increase frequency of monitoring of AST, ALT, bilirubin, alkaline phosphatase and INR (every 48-72 hours or more frequently, as clinically indicated) – Monitor for other clinical symptoms (fatigue, nausea, vomiting, abdominal pain, fever, rash, and/or eosinophilia) 	
 – Contact the Medical Monitor if there are clinical signs of muscle or hepatic injury or other clinical symptoms – Contact the Medical Monitor if there is a concurrent increase of bilirubin, AST, ALT, or alkaline phosphatase from baseline. – Notify the Medical Monitor if there is an AST increase $> 5 \times \text{ULN}$ – Frequency of retesting can decrease to once a week or less if abnormalities stabilize or the trial drug has been discontinued and the subject is asymptomatic – Consider gastroenterology or hepatology referral

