AST or ALT >12 to $\leq 20 \times \text{ULN}$ and Total bilirubin $\leq 2 \times \text{ULN}$ or Isolated total bilirubin > 2 to $\leq 3 \times \text{ULN}$	
 – Delay cabiralizumab therapy per protocol – Increase frequency of monitoring (including but not limited to) of AST, ALT, bilirubin, alkaline phosphatase and INR (every 48-72 hours or more frequently, as clinically indicated) – Monitor for other clinical symptoms (fatigue, nausea, vomiting, abdominal pain, fever, rash, and/or eosinophilia) – Consider imaging to rule out obstruction 	
If AST and ALT $\leq 12 \times \text{ULN}$ for ≤ 28 days:
 
 – Resume routine monitoring – Resume cabiralizumab therapy at same dose level per protocol 
If elevations persist at same level for > 28 days or worsen:
 
 – Discontinue cabiralizumab therapy per protocol – Discuss with Medical Monitor
AST or ALT $> 20 \times \text{ULN}$ or Total bilirubin $>3 \times \text{ULN}$	
 – Discontinue cabiralizumab therapy 	
 – Continue LFT monitoring per protocol until resolution – Continue monitoring for and other associated clinical signs or symptoms

Hepatic Adverse Event Management with Liver Metastasis		
Grade of Liver Test Elevation	Management	Follow-Up
AST or ALT $>3.0 \times \text{ULN}$ and Total bilirubin $>2 \times \text{ULN}$ or INR > 1.5	
 – Discontinue cabiralizumab therapy per protocol 	
 – Continue LFT monitoring per protocol until resolution. – Continue monitoring for and other associated clinical signs or symptoms – Contact the Medical Monitor – Evaluate for non drug related causes of the laboratory abnormalities (e.g. obstruction, viral infection, Gilbert's disease, etc) – Under selected circumstances (e.g alternative etiology is identified), patient may receive additional therapy only after consultation and agreement between the Sponsor/MM and the investigator if receiving additional treatment with cabiralizumab is in the best interest of the patient (e.g if the subject has demonstrated a response to therapy)

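### The DLT exclusion for brief, isolated enzyme rises has lower bounds, so read literally a smaller Grade 3 rise counts as a DLT while a larger one does not

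*Protocol*

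**What the plan says.** Protocol Section 5.1.1.1 sets a default and then lists exceptions. The default begins "A DLT is defined as a study drug-related Non-Hematologic" and takes in any such AE of Grade 3 or higher in the first 28 days. Two of the exceptions matter here.

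- **Enzyme exclusion.** In the absence of symptoms and of accompanying changes in bilirubin or ALT, AST/ALT above 12 and up to 20 times ULN "that last for < 7 days will not be considered a DLT and serum elevations of CK and/or LDH" above 15 and up to 20 times ULN, also for under 7 days, are not DLTs.
- **irAE exclusion.** This covers a "Grade 3 immune-related adverse event (irAE) that resolved to a Grade 1 or less within 14 days". The section then narrows the term: "An irAE is defined as a clinically significant AE that is associated with study drug exposure, of unknown etiology", and consistent with an immune-mediated mechanism.

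The same section sends events to the investigator, the Medical Monitor and the Efficacy and Safety Review Committee "to determine whether they qualify as DLT considering its clinical significance".

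The management tables rank the same laboratory values by severity. For AST/ALT above 5 and up to 12 times ULN with bilirubin no more than 2 times ULN, Appendix 6 says "Continue cabiralizumab therapy if there are no clinical signs of significant muscle or hepatic damage". Above 12 and up to 20 times ULN it says "Delay cabiralizumab therapy per protocol". Appendix 8 continues dosing at CK above 10 times ULN when isoenzymes are normal, and delays it at CK or LDH above 15 and up to 20 times ULN.

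**The concern.** The exclusion has a floor as well as a ceiling. A brief, isolated rise just above the floor is exempt. One just below it, if recorded as a drug-related Grade 3 AE, falls back on the default and is a DLT. The written rule is therefore stricter on the milder event.

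The DLT count drives escalation through Table 5.1.1-1, where single events carry weight. One DLT in 3 subjects changes the decision from E to S, and two in 3 at 2 mg/kg stop enrollment. Both combination cohorts wait until 4 mg/kg monotherapy is confirmed tolerable (Section 5.1.2), so a wrong count holds them back too. The sponsor already lists AST, ALT and CK abnormalities among its other events of interest (SAP Section 7.1.1.1), although neither document gives a frequency.

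**Working it through.** **Step 1: classify example events by the text.** Each event is isolated, asymptomatic, drug-related, under 7 days, recorded as Grade 3 or higher, and outside the irAE exclusion.

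| Event | Enzyme exclusion (Section 5.1.1.1) | Status by the text | Management (Appendices 6 and 8) |
|---|---|---|---|
| AST 8x ULN | not covered (≤12x) | DLT | continue dosing |
| AST 15x ULN | covered | not a DLT | delay |
| CK 12x ULN, isoenzymes normal | not covered (≤15x) | DLT | continue dosing |
| CK 18x ULN | covered | not a DLT | delay |

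The two orderings are opposite.

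**Step 2: the condition on grade.** The table assumes that Grade 3 begins below 12x ULN for AST/ALT and below 15x ULN for CK. The documents print no CTCAE cut-offs; if Grade 3 began at or above those bounds there would be no gap. Two hints favor the assumption without proving it. Appendix 6 has a separate row starting above 5x under its liver-test grade column. Section 8.1.1 refers to Grade 4 CK up to 20x ULN, so Grade 3 CK begins lower than that. No LDH grade is given, so AST/ALT and CK carry the point.

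**Step 3: reproduce the plan's own figure.** The inputs are Table 5.1.1-1 with its accept, stay, de-escalate and re-escalate rules, cohorts of 3, at most 6 per dose, and the Appendix 5 Scenario 1 rates of 0.10 at 2 mg/kg and 0.15 at 4 mg/kg. Exact binomial enumeration gives 3.49 / 10.70 / 85.82% for under 2 mg/kg / 2 mg/kg / 4 mg/kg. Appendix 5 Table 3 states 3.49 / 10.74 / 85.77% from 10,000 simulated trials. These agree.

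**Step 4: add counted gap events.** Let g be the share of subjects with a counted gap event at each dose, independent of other DLTs. Counted means drug-related, recorded as a Grade 3 AE, under 7 days, outside the irAE exclusion and upheld by the committee. The documents give no value for g, so a range is shown.

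Apparent DLT rate = 1 − (1 − base)(1 − g). For g = 0.05:

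- 2 mg/kg: 1 − 0.90 × 0.95 = 0.145
- 4 mg/kg: 1 − 0.85 × 0.95 = 0.1925

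P(E after the first 3 subjects) = P(0 DLTs in 3) = [0.90(1 − g)]³. For g = 0.05 this is 0.855³ = 0.625.

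| g | Rate 2 / 4 mg/kg | E after first 3 | Stop at 2 mg/kg | Select 2 mg/kg | Select 4 mg/kg |
|---|---|---|---|---|---|
| 0 | 0.100 / 0.150 | 72.9% | 3.5% | 10.7% | 85.8% |
| 0.02 | 0.118 / 0.167 | 68.6% | 4.9% | 13.7% | 81.4% |
| 0.05 | 0.145 / 0.1925 | 62.5% | 7.5% | 18.3% | 74.2% |
| 0.10 | 0.190 / 0.235 | 53.1% | 13.1% | 25.6% | 61.3% |

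If such rises occur in 5% of subjects but only half are counted (g = 0.025), selection of 4 mg/kg is 80.2%.

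**The case against.** The strongest reply is that the floors have a visible purpose. The bullet refers to Appendices 6 to 8, and 12x and 15x ULN are where those tables start to delay dosing. A result that interrupts dosing must be recorded as an AE under Section 9.2.6, so the exclusion starts where the tables would themselves create an AE. On this view smaller rises were never meant to be DLTs. That is probably the intent, but the text does not say so, and the default then applies.

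Three provisions narrow the gap.

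- **AE capture.** Where dosing continues, Section 9.2.6 reaches a smaller rise mainly through "Any laboratory test result that is clinically significant or meets the definition of an SAE", or through corrective therapy. Many brief rises need never be recorded as AEs.
- **irAE exclusion.** A rise recorded because it is clinically significant already meets that part of the irAE definition. What remains is a rise not judged immune-mediated, or one that does not reach Grade 1 within 14 days.
- **Committee review.** Discussion of whether an event qualifies is written into the DLT section, and escalation needs committee agreement on all the safety data. A brief rise that sites are told to dose through is an obvious candidate for being set aside. The committee would still be correcting a written rule case by case.

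Two points about the numbers stand. The values of g are assumed and are defined after all these filters. Nothing in Appendix 5 says that its true DLT rates exclude such rises, so adding g may double count. The table shows sensitivity and does not estimate effect.

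The fix is also partial. An AST of 8x ULN lasting 8 days would remain a DLT by default while Appendix 6 continues dosing. Rises of 7 days or more are not inverted, however, because the larger rise is not exempt either.

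**Conclusion.** The concern holds. Read literally, the exclusion exempts the larger brief rise and leaves the smaller one as a DLT, contrary to the protocol's own management tables. This rests on Grade 3 starting below 12x ULN for AST/ALT or 15x ULN for CK, which the documents do not print.

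The defect lies in the wording of the rule that feeds dose escalation. The Appendix 5 selection percentages themselves reproduce. The direction is conservative: the cost is a wrongly delayed or stopped escalation and late or unopened combination cohorts, with no added exposure to a more toxic dose. How often it would happen cannot be derived from the documents. For assumed counted rates of 2% to 10%, selection of 4 mg/kg in Scenario 1 falls by 4.4 to 24.5 percentage points (85.8 − 81.4 and 85.8 − 61.3), an upper-bound illustration. It should be corrected, because the written rule gives the wrong answer and the correction is small.

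**What to change.** Delete the two lower bounds in the enzyme bullet of Section 5.1.1.1. Keeping the existing conditions on symptoms and accompanying changes, it would say that AST/ALT elevations up to 20x ULN, and CK and/or LDH elevations up to 20x ULN, lasting under 7 days are not DLTs. Alternatively, keep the bands and add one sentence that lower elevations meeting the same conditions are likewise not DLTs.

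Either version exempts only rises smaller than those already exempt. It changes one bullet and adds no procedures or patients. Revised Protocol 03 changed this bullet as part of aligning the DLT criteria with other ongoing studies, so the sponsor should check whether their wording has the same floors and needs the same correction.
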